7.2.2 Exclusion Criteria

Patients meeting any of the following criteria at Visit 1 or Visit S-1 will not be eligible for study participation:

Cohort 1:

1. Decompensated liver disease: coagulopathy, history, or presence of clinically significant ascites, variceal hemorrhage, and/or encephalopathy.
2. Sexually active males and females who are not using a reliable contraceptive method with $\leq 1\%$ failure rate (such as hormonal contraception, intra-uterine device, or complete abstinence) throughout the duration of the study and 90 days thereafter (from signed informed consent through 90 days after last dose of study drug). See [Appendix 6](#) for further details.
3. Patients not compliant with treatment in study A4250-005.
4. Any other conditions or abnormalities which, in the opinion of the investigator or Medical Monitor, may compromise the safety of the patient, or interfere with the patient participating in or completing the study.

Cohort 2:

1. Known pathologic variations of the ABCB11 gene that have been demonstrated to result in complete absence of the BSEP protein.
2. Patient with past medical history or ongoing presence of other types of liver disease including, but not limited to, the following:
 - a) Biliary atresia of any kind.

- b) Suspected or proven liver cancer or metastasis to the liver on imaging studies.
- c) Histopathology on liver biopsy is suggestive of alternate non-PFIC related etiology of cholestasis.

Note: Patients with clinically significant portal hypertension are allowed.

- 3. Patient with a past medical history or ongoing presence of any other disease or condition known to interfere with the absorption, distribution, metabolism (specifically bile acid metabolism), or excretion of drugs in the intestine, including but not limited to, inflammatory bowel disease.
- 4. Patient with past medical history or ongoing chronic (i.e., >3 months) diarrhea requiring intravenous fluid or nutritional intervention for treatment of the diarrhea and/or its sequelae.
- 5. Patient has a confirmed past diagnosis of infection with human immunodeficiency virus or other present and active, clinically significant, acute, or chronic infection, or past medical history of any major episode of infection requiring hospitalization or treatment with parenteral anti-infective treatment within 4 weeks of treatment start (Study Day 1) or completion of oral anti-infective treatment within 2 weeks prior to start of Screening Period.

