- 6. Any patient with suspected or confirmed cancers except for basal cell carcinoma, and non-liver cancers treated at least 5 years prior to Screening with no evidence of recurrence.
- 7. Patient has had a liver transplant, or a liver transplant is planned within 6 months of the Screening/Inclusion Visit.
- 8. Decompensated liver disease, coagulopathy, history, or presence of clinically significant ascites, variceal hemorrhage, and/or encephalopathy.
- 9. INR >1.4 (the patient may be treated with Vitamin K intravenously, and if INR is \leq 1.4 at resampling the patient may be included).
- 10. Serum ALT $>10 \times$ upper limit of normal (ULN) at Screening.
- 11. Serum ALT $>15 \times$ ULN at any time point during the last 6 months unless an alternate etiology was confirmed for the elevation.
- 12. Total bilirubin $>10 \times$ ULN at Screening.
- 13. Patient suffers from uncontrolled, recalcitrant pruritic condition other than PFIC. Examples include, but not limited to, refractory atopic dermatitis or other primary pruritic skin diseases.
- 14. Any patient who is pregnant or lactating or who is planning to become pregnant within 72 weeks of the Screening/Inclusion Visit.

15. Sexually active males and females who are not using a reliable contraceptive method with $\leq 1\%$ failure rate (such as hormonal contraception, intrauterine device, or complete abstinence) throughout the duration of the study and 90 days thereafter (from signed informed consent through 90 days after last dose of study drug). See [Appendix 6](#) for further details.
16. Patient with a past medical history of alcohol or substance abuse will be excluded. Patient must agree to refrain from illicit drug and alcohol use during the study.
17. Administration of bile acid or lipid binding resins and medications that slow GI motility (Refer to [Appendix 1](#) – Concomitant Medications Guidelines).
18. Patient has had investigational exposure to a drug, biologic agent, or medical device within 30 days prior to Screening, or 5 half-lives of the study agent, whichever is longer.
19. Any other conditions or abnormalities which, in the opinion of the investigator or Medical Monitor, may compromise the safety of the patient, or interfere with the patient participating in or completing the study.

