10.2.2 Individual Patient Safety Monitoring

10.2.2.1 Liver Monitoring

Strategies to monitor markers of liver disease throughout the study are outlined below where the ULN will be based on central laboratory reference values for age and gender.

For abnormalities classified as hepatic adverse events and/or hepatic decompensation, a PK sample should be collected as close to the onset of the event as possible (PK samples are not required during the screening period).

If isolated transaminase elevations are observed, defined as:

1. Normal bilirubin AND absence of clinical hepatitis symptoms AND
 - ALT or AST $\geq 5 \times$ ULN (if normal at baseline) or an absolute threshold of 800 U/L, whichever comes first
 - OR ALT or AST $\geq 3 \times$ baseline (if abnormal at baseline) or an absolute threshold of 800 U/L, whichever comes first

Then:

- a) Repeat liver profile (AST, ALT, bilirubin, and prothrombin time [PT] or INR) within 2 to 3 days
- b) Evaluate creatine phosphokinase (CPK) and lactate dehydrogenase (LDH)
- c) As needed (for example, persistent ALT/total bilirubin elevation or worsening of liver function), consider evaluation for alternative etiologies

Monitor the patient using close observation found in [Section 10.2.2.2](#).

If any ONE of the following criteria are met:

1. Transaminases (ALT or AST $\geq 3 \times$ baseline or absolute threshold increase of +300 U/L, whichever comes first) AND bilirubin increases to such where total bilirubin $> 2 \times$ ULN if total bilirubin was within normal range at baseline
2. Transaminase elevations alone (ALT or AST $> 5 \times$ ULN for patients that were normal at baseline) or absolute threshold of +300 U/L (for patients starting with transaminases above ULN at baseline) in presence of normal LDH and CPK
3. Total bilirubin increased, unrelated to hemolysis (elevated reticulocyte count) or established genetic diseases, such as Gilbert's syndrome
 - a) Doubling if total bilirubin was < 3 mg/dL (equivalent to 51.3 μ mol/L) at baseline and total bilirubin is greater than $2 \times$ ULN
 - b) OR Increase by > 3 mg/dL (equivalent to 51.3 μ mol/L) if total bilirubin was ≥ 3 mg/dL (equivalent to 51.3 μ mol/L) at baseline
4. INR increase refractory to vitamin K administration
 - a) Increase by > 1.5 if INR was normal at baseline
 - b) OR Increase by > 0.4 if INR was abnormal at baseline

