10.2.2.7 Re-challenge after Discontinuation/Interruption of Study Drug

The DSMB will evaluate the safety data for patients who have discontinued study drug for an extended period on a case-by-case basis to determine whether re-challenge with A4250 is appropriate. The minimal duration of the discontinuation should be at least one to two weeks.

Patients that have discontinued for an extended period and allowed re-challenge by DSMB will use the last labs prior to restart as the new baseline for determining if DILI criteria are met.

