Appendix 5 Guideline for Fat-Soluble Vitamin Supplementation

Appendix 5: Guideline for Fat-Soluble Vitamin Supplementation

Cholestasis predisposes to fat-soluble vitamin deficiencies. Fat-soluble vitamin levels, i.e., vitamins A and E, 25-hydroxy vitamin D, and INR (surrogate for vitamin K) are measured routinely during the study. If a patient has any fat-soluble vitamin level(s) that are out of range, vitamin supplementation adjustments may be required. Below are suggested guidelines for fat-soluble vitamin deficiency treatment [Venkat 20014; Shneider 2012]. Additional patient monitoring and/or treatment strategies may be warranted at the discretion of the investigator.

Target Fat-soluble Vitamin Levels and Replacement Regimens

Vitamin	Target Range (Serum Level)	Supplementation Strategy
A (retinol)	19 to 77 µg/dL* retinol:retinol-binding protein molar ratio > 0.8	Increments of 5000 IU (up to 25,000 to 50,000 IU/day) orally or monthly intramuscular administration of 50,000 IU**
D (25-hydroxy vitamin D)	15 to 45 ng/mL*	Increments of 1200 to 8000 IU orally daily of cholecalciferol or ergocalciferol; alternatively calcitriol at 0.05 to 0.2 µg/kg/day*
E (α tocopherol)	3.8 to 20.3 µg/mL vitamin E:total serum lipids ratio >0.6 mg/g	Increments of 25 IU/kg of d-α-tocopheryl polyethylene glycol – 1000 succinate (TPGS) orally daily (to 100 IU/kg/day)
K (phytonadione)	INR ≤1.2	
 • 1.2 <INR ≤1.5: 2.5 mg vitamin K orally daily • 1.5 <INR ≤1.8: 2.0 to 5.0 mg vitamin K intramuscular and 2.5 mg vitamin K orally daily • INR >1.8: 2.0 to 5.0 mg vitamin K intramuscular and 5.0 mg vitamin K orally daily

*Clinical practice may vary. This is meant as a guidance only and does not override local standard of care. Investigators should provide best case practices for management and treatment

A4250 – IND 130591
EudraCT 2017-002325-38
Module 5: Clinical Study Reports
M5.3.5.1 – Protocol A4250-008

** For further detail regarding age related Tolerable Upper Intake (UL) for preformed vitamin A please refer to page 163 in the European Food Safety Authority guidance: *Tolerable Upper Intake Levels for Vitamins and Minerals*; Scientific Committee on food Scientific Panel on Dietetic Products, Nutrition and Allergies
http://www.efsa.europa.eu/sites/default/files/efsa_rep/blobserver_assets/ndatolerableuil.pdf

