Methodology: This is a Phase 3, multi-center, open-label extension study to investigate the long-term efficacy and safety of a 120 µg/kg/day daily dose of A4250 in patients with PFIC, including episodic forms also referred to as benign recurrent intrahepatic cholestasis (BRIC). Cohort 1 will consist of children with PFIC Types 1 and 2 who have participated in study A4250-005. Cohort 2 will consist of approximately 60 patients with PFIC who have elevated serum bile acids and cholestatic pruritus and who either (1) do not meet eligibility criteria for Study A4250-005 (PEDFIC 1) or (2) are eligible for enrolment in A4250-005 after recruitment of study A4250-005 has been completed. Up to 40 patients post biliary diversion surgery are allowed to participate in Cohort 2. Eligible patients will be enrolled into this open-label extension study and treated with a daily dose of 40 µg/kg/day ¹ or 120 µg/kg/day of A4250 for 72 weeks, or 40 µg/kg/day for the first 12 weeks followed by 120 µg/kg/day for the remaining 60 weeks ¹ . Patients not tolerating the 120 µg/kg/day dose after a minimum of 1 week will have the option to down-titrate to a lower dose (40 µg/kg/day). The patient should return to the higher dose as soon as deemed appropriate by the investigator. More than one upward dose titration (from 40 µg/kg/day directly to 120 µg/kg/day) for the same event is not recommended. Any dose titration should be done in consultation with the sponsor Medical Monitor or designee.				

¹ As of Protocol Amendment 6.1 UK, patients entering Cohort 2 will start treatment at 40 µg/kg/day with the possibility to dose escalate to 120 µg/kg/day after 12 weeks if there is no improvement in pruritus based on investigator judgment.

Name of Sponsor/Company:	Name of Product:	Name of Active Ingredient:
Albireo AB	A4250	A4250

Patients who wish to continue receiving A4250 after 72 weeks, will have the option to remain on treatment until the drug is commercially available, provided continued use is supported by the risk-benefit profile and the subject has not been previously withdrawn or discontinued from the study.
 
The primary analysis will be performed after the last patient (from Cohort 1 or 2) completes the 72-week treatment period. Analyses during the extension period will consist of safety summaries and other evaluations on an ongoing basis per the schedule of assessment for the extension period.
		

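### The INR stopping rule lets patients with a normal baseline INR reach a higher INR on study drug than patients whose baseline was already abnormal

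*Protocol*

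**What the plan says.** Section 10.2.2.1 of the Protocol lists five criteria, any one of which requires study drug to be interrupted. The fourth is headed "INR increase refractory to vitamin K administration" and has two arms. Under 4a the INR must increase by more than "1.5 if INR was normal at baseline"; under 4b it must increase by more than "0.4 if INR was abnormal at baseline". Both arms are worded as a rise from baseline, not as a level to be reached.

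Four other places determine which baselines can occur and how a rising INR is handled:

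- Section 7.2.2, Cohort 2 exclusion 9, bars an INR above 1.4, with one allowance: "the patient may be treated with Vitamin K intravenously, and if INR is" at or below 1.4 on resampling, entry is possible.
- Section 7.2.2, Cohort 1 exclusion 1, gives no INR figure. It excludes "Decompensated liver disease: coagulopathy, history, or presence of clinically significant ascites" and related signs.
- Section 10.2.2.7 resets the baseline after a long interruption: patients cleared for re-challenge "will use the last labs prior to restart as the new baseline for determining if DILI criteria are met".
- Appendix 5 sets an INR target of 1.2 or below and raises vitamin K in steps. Its top step, for INR above 1.8, is "2.0 to 5.0 mg vitamin K intramuscular and 5.0 mg vitamin K orally daily".

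**The concern.** An INR rise that vitamin K does not correct points to failing hepatic synthesis rather than vitamin deficiency. A stopping rule for it should not let a patient who began with normal clotting go further on drug than one who began slightly abnormal. As written, it does.

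The neighbouring interrupt criteria do not behave this way. For bilirubin (criterion 3), doubling from just under 3 mg/dL gives just under 6, and an increase of more than 3 from a baseline of 3 gives more than 6, so the two arms meet. For transaminases (criterion 2), the normal-baseline limit is a level, 5 × ULN, and the abnormal-baseline limit is a rise of 300 U/L. At the boundary the first is the lower when 5 × ULN < ULN + 300, that is, for any ULN below 75 U/L (the ULN is not stated).

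A slip for *increase to more than 1.5* would explain criterion 4a. That is an inference; sites must apply the text as it stands.

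At stake is a liver-safety stopping rule in a mainly paediatric study. Scheduled INR tests can be 14 weeks apart (Week 22 to 36 and Week 46 to 60), so the limit needs to be right when a test is done.

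**Working it through.** **Inputs**

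- Permitted rise, normal baseline: 1.5 (section 10.2.2.1, 4a).
- Permitted rise, abnormal baseline: 0.4 (section 10.2.2.1, 4b).
- Highest Cohort 2 entry INR: 1.4 (section 7.2.2, exclusion 9).
- Top vitamin K step: INR above 1.8 (Appendix 5).
- Normal INR: **assumed** 0.8 to 1.2. The upper end matches the Appendix 5 target, which is a vitamin K target and not a stated laboratory limit. The upper limit is varied from 1.1 to 1.3 below.

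**Formula.** Absolute trigger = baseline INR + permitted rise.

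| Baseline | Arm | Interrupt above |
|---|---|---|
| 0.8 | 4a | 0.8 + 1.5 = 2.3 |
| 1.0 | 4a | 1.0 + 1.5 = 2.5 |
| 1.2 | 4a | 1.2 + 1.5 = 2.7 |
| just above 1.2 | 4b | just above 1.2 + 0.4 = 1.6 |
| 1.3 | 4b | 1.3 + 0.4 = 1.7 |
| 1.4 | 4b | 1.4 + 0.4 = 1.8 |

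The lowest 4a trigger (2.3) is above the highest 4b trigger at a Cohort 2 entry baseline (1.8).

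**Two example patients.** From 1.0 to 2.4 is a rise of 1.4, which does not exceed 1.5, so criterion 4 is not met. From 1.3 to 1.75 is a rise of 0.45, which exceeds 0.4, so drug is interrupted.

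**Dependence on the assumed range**

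- Step at the upper limit of normal U: (U + 1.5) − (U + 0.4) = 1.1, whatever U is.
- A normal-baseline trigger N + 1.5 exceeds 1.8 whenever N > 0.3.
- U = 1.1: 4a runs from 2.3 to 2.6, 4b from 1.5 to 1.8. U = 1.3: 4a runs from 2.3 to 2.8, 4b from 1.7 to 1.8. The order is the same.

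**When the order would reverse.** The abnormal baseline would have to exceed N + 1.1: from 0.8 + 1.1 = 1.9 to 1.2 + 1.1 = 2.3. The 1.4 cap rules this out at Cohort 2 entry. It could arise only in Cohort 1, despite its coagulopathy exclusion, or after a re-challenge baseline reset.

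**Distance from the protocol's own INR marks**

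- Above the Cohort 2 entry limit of 1.4: 4a by 2.3 − 1.4 = 0.9 to 2.7 − 1.4 = 1.3; 4b by 1.6 − 1.4 = 0.2 to 1.8 − 1.4 = 0.4.
- Above the Appendix 5 top step of 1.8: 4a by 2.3 − 1.8 = 0.5 to 2.7 − 1.8 = 0.9. A refractory patient with a normal baseline could be on the highest vitamin K step through that whole interval with study drug continuing.

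**Could another criterion catch it?** Criteria 1, 2, 3 and 5 each need a change in transaminases, bilirubin or both. None gives a numeric stop for an isolated INR rise.

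**The case against.** The strongest defence is that a patient who starts impaired has less reserve, so a smaller permitted rise is reasonable. The protocol has a similar step elsewhere: the isolated-transaminase rule uses 5 × ULN for a normal baseline and 3 × baseline for an abnormal one, so an abnormal baseline below about 1.67 × ULN (5 ÷ 3) is flagged at a lower level. Lesser reserve may well justify a smaller rise. It does not justify a drop of 1.1 at the boundary or a normal-baseline limit of 2.3 to 2.7. The transaminase rule leads to repeat tests and close observation, not interruption, and also carries an absolute limit of 800 U/L.

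Second, other safeguards exist. Appendix 5 escalates vitamin K from INR above 1.2. Section 10.2.2.4 requires a bleeding work-up that includes INR. Section 10.2.2.5 stops treatment for end-organ damage from fat-soluble vitamin deficiency, and section 10.2.2.3 advises against re-challenge after decompensation. Laboratory values are graded for clinical significance, investigators may withdraw a patient, and the DSMB reviews liver values. All this stands and makes it less likely that a child at INR 2.4 would simply continue. But these steps are discretionary, need a clinical event, or do not stop the drug; none is a numeric stop.

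Third, the affected situation is narrow: a normal baseline, a refractory rise and no qualifying transaminase or bilirubin change. The protocol gives no frequency for it, so the practical impact is unknown. No INR is scheduled at Visit 1, so the source of the Cohort 1 baseline is not visible here. The protocol is dated February 2022 with the study planned to end in Q3 2023, so a change would mainly reach remaining Cohort 2 patients. These points limit the benefit but do not make the text correct.

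**Conclusion.** The concern holds. Criterion 4 is wrong as written: patients with a normal baseline INR have the looser absolute stopping level. The drop of 1.1 at the normal/abnormal boundary follows from the text alone. The bands of 2.3 to 2.7 for 4a and 1.6 to 1.8 for 4b are illustrative: they rest on an assumed normal range of 0.8 to 1.2 and, for 4b, on Cohort 2 entry baselines. The direction holds for any plausible normal range and fails only for an abnormal baseline of about 1.9 to 2.3 or more. That the wording is a slip is likely but not proven. The point should be fixed; clinical judgment and the other safeguards reduce its practical effect without replacing the numeric limit.

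**What to change.** Reword 4a as an absolute level no higher than the 4b trigger, and leave 4b unchanged. Two options, with the medical team to confirm the value:

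- *Increase to more than 1.5 if INR was normal at baseline.* From baselines of 0.8 to 1.2 this needs a rise of 1.5 − 0.8 = 0.7 down to 1.5 − 1.2 = 0.3.
- *Increase to more than 1.6*, if a rise of 0.3 from 1.2 is thought too tight. The rise is then 0.8 down to 0.4, and the limit meets 4b exactly at a baseline of 1.2 (1.2 + 0.4 = 1.6).

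Make the same change in any parallel country version with this text. The file also contains a UK version (its synopsis footnote begins "As of Protocol Amendment 6.1 UK, patients entering Cohort 2 will start treatment at 40"), but that version's liver-monitoring section is not shown and should be checked.

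The cost is a protocol amendment with a site letter, because lowering a stopping limit is a substantive safety change, repeated for each country version affected. No tests or visits are added. The downside is possibly a few more temporary interruptions among patients with a normal baseline INR.

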10.2.2.2 Close Observation

- Repeat liver enzyme and serum bilirubin tests two or three times weekly. Frequency of re-testing can decrease to once a week or less if abnormalities stabilize or the trial drug has been discontinued and the patient is asymptomatic
- Obtain a more detailed history of symptoms and prior or concurrent diseases

- Obtain a history of concomitant drug use (including non-prescription medications and herbal and dietary supplement preparations), alcohol use, recreational drug use, and special diets
- Consider ruling out alternate etiology including acute viral hepatitis types A, B, C, D, and E; autoimmune or alcoholic hepatitis; non-alcoholic steatohepatitis; hypoxic/ischemic hepatopathy; and biliary tract disease
- Obtain a history of exposure to environmental chemical agents
- Obtain additional tests to evaluate liver function, as appropriate (e.g., INR, direct bilirubin)
- Consider gastroenterology or hepatology consultations
- Follow subjects with potential drug-induced liver injury (DILI) until the laboratory, and new associated clinical abnormalities have normalized or returned to baseline (enrollment) values or have stabilized (defined as laboratory values being stable for 3 months). Continue to work up for alternate etiologies for the abnormal liver disease as stated above until case has resolved. If imaging changes are found as part of the assessment for etiology, these should be continued to be followed until normalization or returned to baseline or until the investigator feels the changes have stabilized.

10.2.2.3 De-challenge/Re-challenge for Liver and Clinical Hepatitis Monitoring

1. Re-challenge is not recommended:
 - a) If a patient has had possible/probable drug-induced liver injury
 - b) If a decompensation event has occurred (i.e., variceal hemorrhage, ascites, hepatic encephalopathy, etc.).
2. If the event is assessed as due to underlying cholestatic liver disease variability or another alternative etiology is identified AND liver tests returned to baseline, re-challenge may be considered after consultation with the sponsor Medical Monitor.
3. If the ALT/total bilirubin elevations are observed after re-challenge, then repeat re-challenge is discouraged.

If a patient is permanently discontinued, monitoring should be continued as outlined in [Section 10.2.2.8](#).

10.2.2.4 Diarrhea

Study drug should be discontinued if a patient develops diarrhea with at least 1 of the following concomitant signs or symptoms: grossly bloody stools, vomiting, dehydration requiring treatment with oral or intravenous rehydration and/or electrolyte imbalances, fever ($\geq 38^{\circ}\text{C}$) and/or the diarrhea persists for 7 or more days. Patients with prolonged diarrhea (≥ 7 days) should be assessed using hemoccult cards.

Blood in stools or any other signs of bleeding should trigger clinical and laboratory assessment such as measurement of PT/aPTT, INR, platelets, etc. Any deficits should be corrected, as clinically indicated.

Cause of bleeding should be investigated, and an evaluation should be obtained. If there is a reduction in hemoglobin greater than 2 g/dL there should be a discussion with the Medical Monitor and the appropriate work up will be decided. Information needed for this discussion should include presence of any diarrhea, recent iron studies, any signs of gross bleeding and what organs are involved, recent and current complete blood count, INR, any changes in heart rate, blood pressure, weight, last results of imaging and endoscopy/ colonoscopy and recent infectious work up, if done.

If gross blood in stool/bleeding is seen, an AE of blood in stool/bleeding should be reported.

Study drug will be reintroduced (re-challenge) when the symptoms have resolved. If the diarrhea re-occurs within 1 week after the re-challenge with no alternate etiology, the patient will be permanently discontinued and monitored as outlined in [Section 10.2.2.8](#).

